### 6.1.5. Analysis Visit Windows

#### 6.1.5.1. Non-Diary Assessments

Visits will be analyzed as scheduled (i.e., not subject to visit windowing). Unscheduled, early termination, and/or repeated measurements will only be included if a scheduled measurement is not available and the unscheduled, early termination, or repeated measurement falls within the analysis visit windows as described in Table 3 (Cohort 1 [Phase 1]) and Table 4 (Cohort 2 [Phase 2b]). The windows follow the Schedule of Events in Table 1 and Table 2. Visits falling outside of these windows will not be windowed (e.g., an unscheduled visit before first application of study drug). Unscheduled/repeated measurements will be listed.

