4.10 Treatment Stopping Rules

If a subject has non-cutaneous adverse events of concern, clinically significant laboratory values or any condition that the Investigator determines could possibly be related to the investigational product, the Investigator should immediately contact the Medical Monitor to discuss if the subject should be discontinued from treatment with investigational product.

Treatment for any individual subject will be discontinued if the subject experiences:

- A serious adverse event (SAE) or a clinically significant non-serious AE which in the opinion of the Principal Investigator or Medical Monitor warrants discontinuation from the study for that subject's well-being.
- A treatment-emergent severe (Grade 3 or higher) laboratory abnormality (confirmed by repeat sample).
- A severe infection (Grade 3 or higher)
- An Ischemic or thromboembolic cardiovascular event (regardless of Grade)
- Any other adverse event that represents an unacceptable risk to the subject (e.g., Grade 3 or higher)

As noted above, study treatment must be discontinued immediately in the event of a female subject's pregnancy.

Treatment should be interrupted:

- If a subject develops an application site reaction with the clinical appearance of an 'irritation reaction', and with a severity of a Dermal Response Score of 5 (erythema, edema and papules) or greater on the scale of Berger and Bowman, treatment should be interrupted for up to one week and may then be resumed if the reaction has, in the opinion of the Investigator, adequately resolved.

Treatment should be discontinued:

- If the application site reaction reoccurs, treatment should be discontinued permanently, and the subject followed until the reaction resolves.

For cases of suspected allergic contact dermatitis, the Medical Monitor and Sponsor should be notified and there should be discussion about performing patch testing to further evaluate. Patch testing is encouraged in such cases.

Phase 2b (Cohort 2)

In the event of a medical emergency where unblinding is required to provide medical care to the subject, refer to the most current IRT plan and Breaking Treatment Codes ([Section 4.6.1](#)). Contact the Medical Monitor and the Sponsor promptly.

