5.1.6 Laboratory Tests

All tests listed in Table 3 below will be performed according to the Schedule of Visits and Assessments (Section 1.3) unless otherwise noted. The collection of specimens will be in a non-fasting state (no food restrictions). In addition, laboratory safety tests may be performed at various unscheduled time points, if deemed necessary by the Investigator.

Table 3. Laboratory Tests

Hematology	Serum Chemistry

 • Hemoglobin • Hematocrit • Total and differential leukocyte count • Red blood cell count with indices and morphology • Platelet count • Reticulocyte count¹ 	
 • Blood Urea Nitrogen • Bilirubin (total and direct) • Alkaline phosphatase • Aspartate aminotransferase • Alanine aminotransferase • Albumin • Sodium • Potassium • Chloride • Glucose • Creatinine • Creatine kinase
Urinalysis	Additional Tests

 • pH • Specific gravity • Protein² • Glucose • Ketones • Bilirubin • Blood² • Nitrite² • Urobilinogen • Leukocyte esterase² 	
 • Thyroid Stimulating Hormone T4 (TSH/T4) • Urine pregnancy test³ (for females of childbearing potential only) • Serum pregnancy test (hCG)⁴ • Follicle-stimulating Hormone (FSH) ⁵ • Pharmacokinetic (PK) assessments

¹ If red blood cell count, hemoglobin or hematocrit values are below the lower limit of normal, reticulocyte count will be performed

² If urinalysis is positive for protein, blood, nitrite and/or leukocyte esterase, a microscopic examination (for red blood cells, white blood cells, bacteria, casts, and epithelial cells) will be performed.

³ Cohort 1: At Baseline, Day 8, Day 15 and Day 22 for FOCBP only. Cohort 2: At Baseline, Week 4, 8, 12 and 13 for FOCBP only.

⁴ At screening only for FOCBP.

⁵ If indicated to confirm post-menopausal status

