6.3.4 Clinical Laboratory Results and Vital Signs

All clinical laboratory results and ECG measurements and their change from Baseline (pre-dose), will be summarized descriptively by parameter, along with time point of collection.

A shift table describing out-of-normal range shifts will be provided for clinical laboratory results.

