**Table 2: Cohort 2 (Phase 2b)**

Study Procedure	Screen	Baseline Day 1	Wk 2 Day 15	Wk 4 Day 29	Wk 8 Day 57	Wk 12 Day 85	Wk 13 Day 92
Visit	1	2	3	4	5	6	7
Visit Window	-4 weeks		+/- 3 days	+/- 5 days	+/- 5 days	+/- 7 days	+/- 3 days
Informed consent	X						
Demographics	X						
Medical and surgical history	X						
Physical examination a	X	X				X	
Vital signs, height, weight b	X	X	X	X	X	X	X
I/E criteria	X	X					
Randomization		X					
Hematology, Serum Chemistries, UA, TSH/T4 c	X	X		X	X	X	
Resting 12-lead ECG	X			X		X	
BSA, IGA, HECSI d	X	X	X	X	X	X	X
NRS pain, WI-NRS e	X	Completed daily from Day 1 to Week 13 Visit →					
QOLHEQ e	X	X	X	X	X	X	X
Nail dystrophy assessment f		X	X	X	X	X	X
Local Tolerability Assessments g		X	X	X	X	X	
Optional Photography h		X	X	X	X	X	X
Urine pregnancy test i		X		X	X	X	X
Serum pregnancy test i	X						
Follicle-Stimulating Hormone (FSH) j	X						
PK sampling k		X		X		X	
IP application/Subject training in clinic l		X	X	X	X	X	
Dispense IP kit m		X	X	X	X	X	
Dispense/review diary		X	X	X	X	X	
Weigh IP tubes n		X	X	X	X	X	
Compliance calculation o		X	X	X	X	X	
Adverse event assessment p	X	X	X	X	X	X	X
Concomitant medications	X	X	X	X	X	X	X

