## **9.3. Clinical Laboratory Evaluations**

Laboratory test results will be summarized descriptively by treatment and study visit as both observed values and change from baseline values for continuous hematology, chemistry (including thyroid), and urinalysis results. Categorical urinalysis results will be summarized using frequencies by study visit and treatment group within cohort.

The number of subjects with clinical laboratory values below, within, or above the normal range by study visit and in relation to baseline will be tabulated for each clinical laboratory analyte by treatment group within cohort (shift table).

Abnormal results will be flagged in the listings. In addition, pregnancy test results and hormonal laboratory results will be listed.

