Baseline		
n	XX	
Mean (SD)	XX.X (X.XX)	
Median	XX.X	
Min, Max	XX, XX	
Week 1		
n	XX	XX
Mean (SD)	XX.X (X.XX)	XX.X (X.XX)
Median	XX.X	XX.X
Min, Max	XX, XX	XX, XX
Week 2		
n	XX	XX
Mean (SD)	XX.X (X.XX)	XX.X (X.XX)
Median	XX.X	XX.X
Min, Max	XX, XX	XX, XX
Week 3		
n	XX	XX
Mean (SD)	XX.X (X.XX)	XX.X (X.XX)
Median	XX.X	XX.X
Min, Max	XX, XX	XX, XX

*Continue for other parameters. Sort alphabetically by parameter.*

Abbreviations: QD = once daily; SD = standard deviation.  
 Note: Subjects are summarized by treatment received. Results from the thyroid panel are included.  
 Baseline is the last non-missing measurement taken before the first application of study drug.  
 Change from baseline is calculated as result – baseline result.  
 Reference Listings: 16.2.8.1.1, 16.2.8.1.4

Table 14.3.5.1.1.2  
 Cohort 2: Summary of Clinical Chemistry Laboratory Results (Standard Units) by Study Visit  
 Safety Population

Study Visit Statistic	Cohort 2					
	ARQ-252 Cream 0.3% QD (N=XX)		ARQ-252 Cream 0.3% BID (N=XX)		ARQ-252 Cream 0.1% QD (N=XX)	
	Observed	Change	Observed	Change	Observed	Change
Baseline						
n	XX		XX		XX	
Mean (SD)	XX.X (X.XX)		XX.X (X.XX)		XX.X (X.XX)	
Median	XX.X		XX.X		XX.X	
Min, Max	XX, XX		XX, XX		XX, XX	
Week 4						
n	XX	XX	XX	XX	XX	XX
Mean (SD)	XX.X (X.XX)	XX.X (X.XX)	XX.X (X.XX)	XX.X (X.XX)	XX.X (X.XX)	XX.X (X.XX)
Median	XX.X	XX.X	XX.X	XX.X	XX.X	XX.X
Min, Max	XX, XX	XX, XX	XX, XX	XX, XX	XX, XX	XX, XX
Week 8						
n	XX	XX	XX	XX	XX	XX
Mean (SD)	XX.X (X.XX)	XX.X (X.XX)	XX.X (X.XX)	XX.X (X.XX)	XX.X (X.XX)	XX.X (X.XX)
Median	XX.X	XX.X	XX.X	XX.X	XX.X	XX.X
Min, Max	XX, XX	XX, XX	XX, XX	XX, XX	XX, XX	XX, XX
Week 12						
n	XX	XX	XX	XX	XX	XX
Mean (SD)	XX.X (X.XX)	XX.X (X.XX)	XX.X (X.XX)	XX.X (X.XX)	XX.X (X.XX)	XX.X (X.XX)
Median	XX.X	XX.X	XX.X	XX.X	XX.X	XX.X
Min, Max	XX, XX	XX, XX	XX, XX	XX, XX	XX, XX	XX, XX

**Repeat this page for the remaining study drugs (Vehicle Cream QD and Vehicle Cream BID), showing the same study visits shown here. Continue for other parameters.**  
 Sort alphabetically by parameter.

Abbreviations: BID = twice daily; QD = once daily; SD = standard deviation.  
 Note: Subjects are summarized by treatment received. Results from the thyroid panel are included. Baseline is the last non-missing measurement taken before the first application of study drug. Change from baseline is calculated as result – baseline result.  
 Reference Listings: 16.2.8.1.1, 16.2.8.1.4

Table 14.3.5.1.2.1  

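### SAP 6.1.5.1 keeps off-schedule lab and ECG values out of the lab and ECG summary tables, and no worst-post-baseline summary picks them up

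*SAP*

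**What the plan says.** **The rule.** SAP 6.1.5.1 analyses scheduled visits as scheduled, without windowing. For anything else, "Unscheduled, early termination, and/or repeated measurements will only be included if a scheduled measurement is not available", and then only if the value falls in a window of Table 3 (Cohort 1) or Table 4 (Cohort 2). Of the remainder it says: "Unscheduled/repeated measurements will be listed". SAP 6.1.8 adds that all collected data go into listings. The rule covers every non-diary assessment, so labs and ECGs fall under it.

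**The schedule.** In SAP Table 2, the Cohort 2 row for "Hematology, Serum Chemistries, UA, TSH/T4" is marked at Screening, Baseline and Weeks 4, 8 and 12. ECGs are marked at Screening and Weeks 4 and 12. Neither is scheduled at Week 2 or Week 13.

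**The tables.** SAP 9.3 defines the shift table as "The number of subjects with clinical laboratory values below, within, or above the normal range by study visit", set against baseline. SAP 9.5 presents ECG measures and interpretation by visit. The shell "Cohort 2: Summary of Clinical Chemistry Laboratory Results (Standard Units) by Study Visit" (Table 14.3.5.1.1.2) has Baseline and Weeks 4, 8 and 12, and the shift shell (14.3.5.1.2.2) has Weeks 4, 8 and 12. Haematology and quantitative urinalysis reuse these shells. The Cohort 2 ECG tables (14.3.6.4.1.2 and 14.3.6.4.2.2) have Baseline and Weeks 4 and 12. SAP 13.1.3.4, the place for abnormal laboratory value tables, reads NA.

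**Off-schedule samples are foreseen.** Protocol 5.1.6 says that "laboratory safety tests may be performed at various unscheduled time points, if deemed necessary by the Investigator". Protocol 5.6 provides unscheduled visits for repeating abnormal tests, and one of the stopping rules in Protocol 4.10 depends on a repeat sample confirming a laboratory abnormality of Grade 3 or above.

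**The concern.** Preferring the scheduled value is sensible for efficacy visits and for by-visit means, where one value per subject per visit is wanted. Safety data differ: a symptom or an abnormal result is often what prompts an extra sample, so the off-schedule value can be the extreme one.

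Protocol 2.4.2 names cytopenias and liver, thyroid and creatine phosphokinase abnormalities among the expected risks, and Protocol 2.3 states that this is the first human study of the cream. If a peak value is found between visits, or in the first three weeks of Cohort 2, a reader comparing arms in the lab and ECG tables will not see it. Listings show the value but give no count by arm.

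The subjects most exposed are those who stop early. The first scheduled post-baseline lab in Cohort 2 is Day 29 ± 5 days, so Day 24 at the earliest. A subject who stops on Day 10 for a laboratory abnormality, and has no later scheduled sample, gives no post-baseline value from Days 2–22 to any lab table. The shift table could show that subject only as *Missing*.

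**Working it through.** The plan gives no figure to reproduce. The check maps each study day to its analysis window and asks whether the table shells have a column for that window.

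**Inputs.** Cohort 2 windows (SAP Table 4): Week 2 = Days 2–22, Week 4 = 23–42, Week 8 = 43–70, Week 12 = 71–90, Week 13 = Day 91 onward. Cohort 1 windows (SAP Table 3): Week 1 = Days 2–11, Week 2 = 12–18, Week 3 = Day 19 onward. Columns come from the shells in SAP 14.2. The last day is taken as the planned final visit: Day 92 in Cohort 2, Day 22 in Cohort 1.

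**Denominators.** Cohort 2: 92 − 2 + 1 = 91 days. Cohort 1: 22 − 2 + 1 = 21 days.

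| Data | Post-baseline columns | Days with no column | Count |
|---|---|---|---|
| Cohort 2 labs | Weeks 4, 8, 12 | 2–22, 91–92 | 21 + 2 = 23 of 91 (25%) |
| Cohort 2 ECG | Weeks 4, 12 | 2–22, 43–70, 91–92 | 21 + 28 + 2 = 51 of 91 (56%) |
| Cohort 1 labs | Weeks 1, 2, 3 | none | 0 of 21 |
| Cohort 1 ECG | Week 2 | 2–11, 19–22 | 10 + 4 = 14 of 21 (67%) |

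If the Cohort 2 final visit falls at the end of its 3-day window (Day 95), the counts are 26 of 94 for labs (28%) and 54 of 94 for ECG (57%). All of these count calendar days on which an off-schedule value would have no column. They do not count results.

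**Days that do have a column.** An unscheduled Cohort 2 lab on Days 23–42 maps to Week 4. If the scheduled Week 4 sample exists, that sample is used and the unscheduled one is only listed. The same holds in the other windows.

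**Confirming repeats.** If the first abnormal value is a scheduled one, it stays in the by-visit summary (including Min and Max) and in the shift table, so leaving out the repeat loses no abnormal subject. If the first abnormal value is itself off schedule, both it and its repeat stay out, unless the scheduled sample is missing and the window has a column. In either case the shift categories are low, normal and high, so no lab table shows a grade or a confirmation.

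**Other lab or ECG tables.** None is free of visit: summaries, shifts and ECG interpretation are all by visit, 13.1.3.4 is NA, and no worst-value row appears in any shell.

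**The case against.** The strongest counter-argument is that the adverse event tables offer a second route. Protocol 5.7.1 allows an abnormal laboratory finding to be an adverse event, 5.7.4 has the investigator evaluate clinically significant values, and 5.7.5 grades events. SAP 9.1 tabulates treatment-emergent events by arm and severity with no restriction to scheduled visits, and Table 14.3.1.5 covers events leading to drug discontinuation. A reader might infer that the worst values vanish from every summary, or that the confirmed Grade 3 stopping threshold is counted nowhere. The documents do not support either: such an event, if recorded, is tabulated by arm. What remains is that this depends on the investigator recording it, and it shows a term and a grade but not the measured value.

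Four further objections stand in whole or part:

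- **Scale.** A reader might take the 25% above as lost data. It is not. Scheduled results are never windowed out. Early-termination visits follow the final-visit procedures (Protocol 5.5), which in Cohort 2 include no labs or ECG, so few routine early-termination values are expected.
- **Bias.** One might infer that arm comparisons are pushed towards no difference. That is not shown. Symptom-driven testing can itself differ between arms, and safety analysis is descriptive (SAP 9).
- **Protocol conflict.** Protocol 6.3.4 opens with "All clinical laboratory results and ECG measurements and their change from Baseline (pre-dose), will be summarized", which could be read as a promise that the SAP breaks. The sentence goes on to describe summaries by parameter and collection time point, and the section then asks for an out-of-range shift table. The SAP supplies both; a worst-value table was never promised.
- **Visibility.** Off-schedule values are listed, abnormal ones are flagged (SAP 9.3), and safety data are reviewed as the study runs (Protocol 6.1.3). That makes the values traceable, but it does not give counts by arm.

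**Conclusion.** The point holds as a limited reporting gap. By its stated rule, the SAP keeps off-schedule lab and ECG values, which the protocol expects to occur, out of the lab and ECG summary tables in two situations: when a scheduled value exists for the visit, and when the window has no column. No worst-post-baseline summary makes up for it. The missing lab columns are a Cohort 2 matter only; for ECGs, Cohort 1 has uncovered days too.

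The size cannot be stated in results or subjects, because the documents neither give nor bound the number of off-schedule tests. No scheduled value is lost, and no direction of bias can be claimed. The conclusion rests on reading 6.1.5.1 as covering safety data, which its heading and wording do without exception, and on the shells being the full set of planned tables. It is worth correcting because the data are already collected and listed.

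**What to change.** Keep the SAP 6.1.5.1 rule for efficacy and for by-visit summaries, and leave the by-visit tables as they are.

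- In SAP 9.3, add a worst-post-baseline row by arm to the lab shift tables (low/normal/high), using all scheduled, unscheduled, repeat and early-termination values.
- In SAP 9.5, add the same row to the ECG interpretation tables.
- For gradable lab parameters, add the maximum post-baseline CTCAE grade by arm, with a count of subjects whose Grade 3 or higher value was confirmed by repeat. Use version 5.0, as in Protocol 5.7.5, and reconcile the version 4.0 cited in the footnotes of the SAP adverse event shells (for example Tables 14.3.1.1, 14.3.1.3 and 14.3.3.1).

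The cost is extra programming and a new derivation, since lab results are not graded in any current table. Nothing changes in visits or data collection. Because symptom-driven testing may differ between arms, the new rows should be labelled descriptive and read beside the by-visit tables.

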**Table 3: Analysis Visit Windows (Cohort 1 [Phase 1])**

Visit Name	Analysis Visit Number	Target Start Day	Lower Limit	Upper Limit
Week 1	2	8	2	11
Week 2	3	15	12	18
Week 3	4	22	19	--

**Table 4: Analysis Visit Windows (Cohort 2 [Phase 2b])**

Visit Name	Analysis Visit Number	Target Start Day	Lower Limit	Upper Limit
Week 2	3	14	2	22
Week 4	5	28	23	42
Week 8	6	56	43	70
Week 12	7	85	71	90
Week 13	8	92	91	--

#### 6.1.5.2. Diary Assessments (WI-NRS, Pain NRS)

Diary entries will be assigned to a study week for analysis based on the study day relative to the first application of study drug according to Table 5 (Cohort 1 [Phase 1]) and Table 6 (Cohort 2 [Phase 2]).

**Table 5: Analysis Visit Windows (Cohort 1 [Phase 1])**

Visit Name	Analysis Visit Number	Lower Limit	Upper Limit
Study Week 1	101	1	7
Study Week 2	102	8	14 #

# Data may have been collected for subjects past Day 14; any Diary entries recorded after this day will not be presented in any summaries. However, all Diary entries will be presented in the data listings; entries after Day 14 will be presented as Week >2.

**Table 6: Analysis Visit Windows (Cohort 2 [Phase 2b])**

Visit Name	Analysis Visit Number	Lower Limit	Upper Limit
Study Week 1	101	1	7
Study Week 2	102	8	14
Study Week 3	103	15	21
Study Week 4	104	22	28
Study Week 5	105	29	35
Study Week 6	106	36	42
Study Week 7	107	43	49
Study Week 8	108	50	56
Study Week 9	109	57	63
Study Week 10	110	64	70
Study Week 11	111	71	77
Study Week 12	112	78	84
Study Week 13	113	85	91 #

# Data may have been collected for subjects past Day 91; any Diary entries recorded after this day will not be presented in any summaries. However, all Diary entries will be presented in the data listings; entries after Day 91 will be presented as Week >13.

### 6.1.6. Pooling of Sites

Sites will be pooled for statistical analysis as follows. For analysis, sites should have a minimum of 10 randomized subjects. The smallest sites will be grouped sequentially in order of smallest to largest within each country, restricting to those sites that did not meet the minimum enrollment of 10, until each pooled site has a minimum of 10 subjects within each country with at least 1 subject in each treatment group.

### 6.1.7. Derived Variables

- **Study Week** = 7-day periods starting on Day 1, as described in [Section 6.1.5.2](#). For example, Study Week 1 corresponds to Days 1 to 7. This is in contrast to **Study Visit**, which describes the actual clinic visit week. The nomenclature of “Study Week” will be used with respect Pain NRS and WI-NRS analyses; otherwise, “Study Visit” will be used.
- **IGA Improvement** = achievement of at least a 2-point improvement (i.e., reduction) in IGA score from baseline.
- **IGA Success** = post-baseline IGA of “Clear” or “Almost Clear” PLUS achievement of at least a 2-point improvement (i.e., reduction) in IGA score from baseline.
- **Average Weekly WI-NRS Pruritus Score** = WI-NRS pruritus scores will be assigned to a particular study week based on the study week window, as shown in [Section 6.1.5.2](#). If 2 or more observations are present for a single day, those observations will be averaged into a single daily value before calculating the average weekly score. The average of the reported (non-missing) WI-NRS pruritus scores assigned to each study week will be calculated. If at least 1 WI-NRS pruritus score is present in this time period, the average weekly WI-NRS pruritus score will be calculated; otherwise the average weekly score will be missing for that week.
- **WI-NRS 4-point Reduction** = achievement of a 4-point reduction in WI-NRS pruritus score at each study week compared to baseline, calculated only for subjects with a WI-NRS pruritus score of  $\geq 4$  at baseline (PRU4 population).
- **HECSI Fingertips Subscore** =  $(E + I + V + F + S + O) * Ex$ ,  
where E, I, V, F, S, and O, are erythema, infiltration/papulation, vesicles, fissures, scale, and oedema, respectively, scored on a scale of 0 to 3 (none to severe); Ex is estimated area of skin involved, graded on a scale of 0 to 4. The range for the HECSI Fingertips subscore is 0 to 72. If any of the component scores are missing, the HECSI Fingertips subscore cannot be calculated; however, if the estimated area of skin involved = 0, the HECSI Fingertips subscore will be set to 0. Lower scores indicate better outcomes.
- **HECSI Fingers (except tips) Subscore** =  $(E + I + V + F + S + O) * Ex$ ,  
where E, I, V, F, S, and O, are erythema, infiltration/papulation, vesicles, fissures, scale, and oedema, respectively, scored on a scale of 0 to 3 (none to severe); Ex is estimated area of skin involved, graded on a scale of 0 to 4. The range for the HECSI Fingers (except tips) subscore is 0 to 72. If any of the component scores are missing, the HECSI Fingers (except tips) subscore cannot be calculated; however, if the estimated area of skin

involved = 0, the HECSI Fingers (except tips) subscore will be set to 0. Lower scores indicate better outcomes.

- **HECSI Palm of Hands Subscore** =  $(E + I + V + F + S + O) * Ex$ ,  
where E, I, V, F, S, and O, are erythema, infiltration/papulation, vesicles, fissures, scale, and oedema, respectively, scored on a scale of 0 to 3 (none to severe); Ex is estimated area of skin involved, graded on a scale of 0 to 4. The range for the HECSI Palm of Hands subscore is 0 to 72. If any of the component scores are missing, the HECSI Palm of Hands subscore cannot be calculated; however, if the estimated area of skin involved = 0, the HECSI Palm of Hands subscore will be set to 0. Lower scores indicate better outcomes.
- **HECSI Back of Hands Subscore** =  $(E + I + V + F + S + O) * Ex$ ,  
where E, I, V, F, S, and O, are erythema, infiltration/papulation, vesicles, fissures, scale, and oedema, respectively, scored on a scale of 0 to 3 (none to severe); Ex is estimated area of skin involved, graded on a scale of 0 to 4. The range for the HECSI Back of Hands subscore is 0 to 72. If any of the component scores are missing, the HECSI Back of Hands subscore cannot be calculated; however, if the estimated area of skin involved = 0, the HECSI Back of Hands subscore will be set to 0. Lower scores indicate better outcomes.
- **HECSI Wrists Subscore** =  $(E + I + V + F + S + O) * Ex$ ,  
where E, I, V, F, S, and O, are erythema, infiltration/papulation, vesicles, fissures, scale, and oedema, respectively, scored on a scale of 0 to 3 (none to severe); Ex is estimated area of skin involved, graded on a scale of 0 to 4. The range for the HECSI Wrists subscore is 0 to 72. If any of the component scores are missing, the HECSI Wrists subscore cannot be calculated; however, if the estimated area of skin involved = 0, the HECSI Wrists subscore will be set to 0. Lower scores indicate better outcomes.
- **HECSI Total Score** = sum of HECSI Fingertips, Fingers (except tips), Palm of Hands, Back of Hands, and Wrists subscores. The range for the HECSI Total score is 0 to 360. Lower scores indicate better outcomes.
- **HECSI-75** = achievement of a 75% reduction in HECSI total score from baseline.
- **Average Weekly Pain NRS Score** = Pain NRS scores will be assigned to a particular study week based on the study week window, as shown in [Section 6.1.5.2](#). If 2 or more observations are present for a single day, those observations will be averaged into a single daily value before calculating the average weekly score. The average of the reported (non-missing) Pain NRS scores assigned to each study week will be calculated. If at least 1 Pain NRS score is present in this time period, the average weekly Pain NRS score will be calculated; otherwise the average weekly score will be missing for that week.
- **Pain NRS 4-point Reduction** = achievement of a 4-point reduction in Pain NRS score at each study week compared to baseline, calculated only for subjects with a Pain NRS score of  $\geq 4$  at baseline (PNRS4 population).

- **QOLHEQ Symptoms Subscore** = sum of QOLHEQ questions 1, 6, 9, 11, 20, 23, and 28. Questions 1, 6, 9, 11, 20, and 23 are scored such that never = 0, rarely = 1, sometimes = 2, often = 3, and all the time = 4; question 28 is scored such that never = 0, rarely = 1, sometimes = 1, often = 2, and all the time = 3. The range for QOLHEQ Symptoms subscore is 0 to 27, where lower scores indicate better outcomes. If 1 question has a missing result, set the missing result to 0 before summing; if more than 1 question is missing, then the QOLHEQ Symptoms subscore cannot be calculated.
- **QOLHEQ Emotions Subscore** = sum of QOLHEQ questions 5, 8, 10, 16, 19, 21, 27, and 30. Questions 5, 8, 16, 19, 21, 27, and 30 are scored such that never = 0, rarely = 1, sometimes = 2, often = 3, and all the time = 4; question 10 is scored such that never = 0, rarely = 1, sometimes = 1, often = 2, and all the time = 3. The range for QOLHEQ Emotions subscore is 0 to 31, where lower scores indicate better outcomes. If 1 question has a missing result, set the missing result to 0 before summing; if more than 1 question is missing, then the QOLHEQ Emotions subscore cannot be calculated.
- **QOLHEQ Limitations in Functioning Subscore** = sum of QOLHEQ questions 2, 3, 12, 14, 15, 17, 25, and 29. All questions are scored such that never = 0, rarely = 1, sometimes = 2, often = 3, and all the time = 4. The range for QOLHEQ Limitations in Functioning subscore is 0 to 32, where lower scores indicate better outcomes. If 1 question has a missing result, set the missing result to 0 before summing; if more than 1 question is missing, then the QOLHEQ Limitations in Functioning subscore cannot be calculated.
- **QOLHEQ Treatment and Prevention Subscore** = sum of QOLHEQ questions 4, 7, 13, 18, 22, 24, and 26. Questions 7, 13, 18, 22, 24, and 26 are scored such that never = 0, rarely = 1, sometimes = 2, often = 3, and all the time = 4; question 4 is scored such that never = 0, rarely = 1, sometimes = 1, often = 2, and all the time = 3. The range for QOLHEQ Treatment and Prevention subscore is 0 to 27, where lower scores indicate better outcomes. If 1 question has a missing result, set the missing result to 0 before summing; if more than 1 question is missing, then the QOLHEQ Treatment and Prevention subscore cannot be calculated.
- **QOLHEQ Total Score** = sum of all 30 QOLHEQ questions. Questions 4, 10, and 28 are scored such that never = 0, rarely = 1, sometimes = 1, often = 2, and all the time = 3; otherwise, questions are scored such that never = 0, rarely = 1, sometimes = 2, often = 3, and all the time = 4. The range for QOLHEQ Total score is 0 to 117, where lower scores indicate better outcomes. If 1 to 3 questions have a missing result, set the missing result to 0 before summing; if more than 3 questions are missing, then the QOLHEQ Total score cannot be calculated.
- **Total Hand % BSA Affected by Disease** = sum of % BSA affected by disease from the following hand areas: left palmar, left dorsal, right palmar, and right dorsal. All 4 hand areas must have a result for the total hand % BSA affected by disease to be calculated.
- **Compliance** = number of applications divided by the expected number of investigational product (IP) applications for each subject. Compliance will be calculated using drug accountability data over the entire treatment period for each subject, up to treatment completion or discontinuation.

- **Number of Expected IP Applications (BID dosing)** = 170 (Cohort 2 BID) for subjects who complete the study or number of days between first and last application of IP, derived as  $2 * (\text{last treatment date} - \text{first treatment date} + 1)$ , for subjects who discontinue early from the study.
- **Number of Expected IP Applications (QD dosing)** = 30 (Cohort 1) or 85 (Cohort 2 QD) for subjects who complete the study or number of days between first and last application of IP, derived as  $(\text{last treatment date} - \text{first treatment date} + 1)$ , for subjects who discontinue early from the study.
- **Number of IP Applications** = number of expected IP applications – missed IP applications as collected in the electronic case report form (eCRF).
- **Weight of IP (g)** = returned tube weight – dispensed tube weight.
- **Body Mass Index (BMI) ( $\text{kg}/\text{m}^2$ )** =  $[\text{weight (kg)} / \text{height (cm)} / \text{height (cm)}] \times 10,000$ .
- **Change from Baseline** = value at current time point – value at baseline.
- **Treatment Emergent AE (TEAE)** = any AE with an onset date/time after the first application of IP. If time is unavailable, any AE occurring on or after the date of first application of IP will be considered treatment emergent.
- **Completion of Study** = Completion of the primary efficacy assessment (IGA) at Week 12. This may differ than what was recorded in the eCRF.

